## 7.3.2 Efficacy of Palovarotene

The phase III study, PVO-1A-301, evaluated the efficacy and safety of the chronic/flare-up palovarotene treatment regimen in reducing new HO as compared with data from the NHS, Study PVO-1A-001. The NHS was an international, 3-year, longitudinal, non-interventional study in 114 participants with FOP with R206H mutation; 98 participants provided at least one post-baseline assessment. All WBCT images from treated participants in Study PVO-1A-301 and untreated participants in the NHS were read in a manner blinded to study origination. Of the 107 participants enrolled in Study PVO-1A-301, 99 had the R206H mutation and 8 had other FOP mutations. Of the 99 with the R206H mutation, 97 had at least one post-baseline HO volume measurement and were included in the Full Analysis Set. The treatment groups assessed in the chronic/flare-up regimen were well matched for baseline demographics.

The median age (range) of participants in the overall population in the palovarotene group (N=99) and in the untreated group (N=111) was 13 (4, 61) and 15 (4, 56) years, respectively. There were more male than female participants in both the palovarotene (53.5% and 46.5%, respectively) and untreated (54.1% and 45.9%, respectively) groups.

Post-hoc analyses showed that mean annualised new HO volume in the overall population was 60% lower in participants receiving the chronic/flare-up palovarotene regimen (9427 mm³) versus untreated participants from the NHS (23 720 mm³).

[figure not shown]
The weighted linear mixed effects (wLME) analysis showed 54% lower fitted mean annualised new HO volume in palovarotene-treated participants (9367 mm^3) versus untreated participants in the NHS (20 273 mm^3) yielding 2-sided nominal p-value p=0.0392.

The median age (range) of participants in the target  $\geq 8/10$  years population in the palovarotene group (N=79) and in the untreated group (N=88) was 14 (8, 61) and 18 (9, 56) years, respectively. There were more male than female participants in both the palovarotene (54.4% and 45.6%, respectively) and untreated (51.1% and 48.9%, respectively) groups.

The mean annualised new HO volume in the target  $\geq 8/10$  years population in palovarotene-treated and untreated participants is shown in Figure 1. Results were similar to the overall population, with the mean annualised new HO volume in palovarotene-treated participants (11 419 mm³) 56% lower than that observed in untreated participants (25 796 mm³). The wLME analysis showed 49% lower fitted mean annualised new HO volume in palovarotene-treated participants (11 033 mm³) versus untreated participants in the NHS (21 476 mm³), yielding 2-sided nominal p-value p=0.1124.

PAGE 32 OF 287

Figure 1 Mean Annualised New HO Volume in Study PVO-1A-301 (≥8/10 years)

HO=heterotopic ossification; SE=standard error.

Note: Figure summarises mean observed annualised new HO.

# 7.4 Registry Study Rationale

Ipsen will implement an observational, prospective and retrospective registry study, which is intended primarily to collect and assess real-world safety data on paediatric and adult participants with FOP exposed to palovarotene and secondly to describe the effectiveness of this treatment, including its effect on physical function. In addition, this study aims to descriptively compare key safety outcomes between participants with FOP exposed and unexposed to palovarotene enrolled in the FOPal registry.

PAGE 33 OF 287

## 8 RESEARCH QUESTION AND OBJECTIVES

## 8.1 Research Question

The aim of the FOPal registry study is primarily to collect and assess real-world safety data on paediatric and adult participants with FOP exposed to palovarotene and secondly to describe the effectiveness of palovarotene in exposed participants, including its effect on physical function. In addition, this study aims to descriptively compare key safety outcomes (i.e. flare-up episodes, growth and bone fractures) between exposed and unexposed participants.

# 8.2 Objectives

## 8.2.1 Primary Objective

To collect and assess real-world safety data in participants with FOP exposed to palovarotene.

# 8.2.2 Secondary Objectives

For participants with FOP exposed and unexposed to palovarotene:

- To describe the range of motion (ROM) as assessed by the Cumulative Analogue Joint Involvement Scale (CAJIS) for FOP;
- To describe the use of assistive devices and adaptations for daily living;
- To describe the physical function using age-appropriate forms of the Fibrodysplasia Ossificans Progressiva-Physical Function Questionnaire (FOP-PFQ);
- To describe the parameters of lung function (observed and % predicted forced vital capacity (FVC), observed and % predicted forced expiratory volume in one second (FEV1), absolute and % predicted FEV1/FVC ratio, observed and % predicted diffusion capacity of the lung for carbon monoxide (DLCO)) at Baseline and over time;
- To describe the physical and mental health (participants ≥15 years old) and overall quality of life (QoL) (participants <15 years old) using age-appropriate forms of the Patient-Reported Outcomes Measurement Information System (PROMIS) Global Health Scale;
- To describe the flare-up frequency;
- To describe any movement mobility change by body location and annually;
- To describe the number of locations impacted by movement mobility change per participant annually;
- To describe the movement mobility outcomes (change in extra bone growth and change in movement), causes and associated symptoms if preceded by a flare-up event by body location;
- To describe the frequency, severity, outcome and descriptive details of any fractures (including bone fracture and vertebral fractures).
- To describe the incidence of pregnancy.

For participants with FOP exposed to palovarotene who become pregnant while enrolled in FOPal:

- To describe pregnancy characteristics and outcomes;
- To describe pregnancy-related AEs through the first year postpartum;
- To describe birth and developmental outcomes through the infant(s)' first year of life.

# REGISTRY STUDY PROTOCOL: VERSION 8.0: 16 APRIL 2025

PAGE 34 OF 287

For growing children with FOP exposed and unexposed to palovarotene:

- To describe linear height and knee height velocities until skeletal maturity or final adult height is reached;
- To describe linear height z-scores until skeletal maturity or final adult height is reached;
- To describe the difference between chronological age and bone age;
- To describe the frequency, severity and descriptive details of PPC.

For participants with FOP exposed to palovarotene:

• To describe the use (dose and frequency) of palovarotene in the real-world setting.

**PAGE 35 OF 287** 

#### 9 RESEARCH METHODS

[figure not shown]
# 9.1 Registry Study Design

FOPal is an observational, prospective and retrospective registry study designed to collect and assess real-world safety data on paediatric and adult participants with FOP exposed to palovarotene and secondly to describe the effectiveness of palovarotene in exposed participants. Additionally, key safety outcomes (i.e. flare-up episodes, growth and bone fractures) will be descriptively compared in participants with FOP exposed and unexposed to palovarotene enrolled in the FOPal registry.

Exposed and unexposed participants will be recruited in countries/sites willing to participate and where palovarotene is registered/marketed. For exposed participants, the decision to prescribe palovarotene will be made prior to and independently of the decision to enrol the patient in the FOPal registry study.

Participants who started palovarotene treatment before the implementation of the registry study in their country may also be enrolled. All participants who received at least one dose of palovarotene treatment before enrolling in the registry study (i.e. signing the informed consent) will be considered non-naïve. In such context, some data will be collected retrospectively from the first dose of marketed palovarotene intake. A schematic representation of the different data collection scenarios is shown Figure 2.

Figure 2 Schematic representation of the different scenarios applied for prospective and retrospective data collection from participants enrolled in the FOPal registry

The schedule of assessments in Table 2 and Table 3 describes the type of data collected for exposed naïve and non-naïve participants, respectively, from the first dose of marketed palovarotene intake. The schedule of assessments in Table 4 describes the type of data collected for unexposed participants from up to 12 months before the ICF signature. The details are described in the Section 9.2.7.

**PAGE 36 OF 287** 

As this is a non-interventional, observational registry study designed to collect and assess real-world data, exposed participants will receive palovarotene as prescribed by their treating physician, as per local label. Palovarotene will be supplied to the participant according to usual practice, not by the sponsor.

In addition, participants will be treated in accordance with usual medical practice during their participation in the FOPal registry study. No additional assessments or tests will be required by this protocol. All relevant data collected as part of routine medical care will be captured using the electronic Case Report Form (eCRF) by the investigator (patient-reported questionnaires will be completed directly by the participant on paper and returned to the site for data entry into the eCRF) and transmitted to the sponsor. If some assessments are not routinely performed by the investigator, they will not complete the corresponding sections in the eCRF.

The FOPal registry study will collect data at Baseline and at each Follow-up Visit. Follow-up Visits are scheduled as per routine clinical practice (recommended every 6 months).

The duration of the FOPal registry study is up to 11 years, with an enrolment period of maximum 10 years from first participant, first visit, and a minimum of 1 year of data collected for participants who are enrolled within that period.

The primary objective of the FOPal registry study is to collect and assess real-world safety data in participants with FOP exposed to palovarotene, to permit the description and incidence of all treatment-emergent adverse events (TEAEs), serious TEAEs and nonserious TEAEs, whether or not they are considered related to palovarotene and all serious and nonserious treatment-related TEAEs.

Secondary objectives include collecting real-world data to describe the effectiveness of palovarotene on ROM, use of assistive devices and adaptations for daily living, physical function, lung function and physical and mental health (or overall QoL in participants <15 years old). Specifically, any movement mobility change, the number of impacted locations and the movement mobility outcomes will also be described, as well as the use of palovarotene (dose, frequency) in the real-world setting. Incidence of pregnancy, outcomes of pregnancies, AEs related to pregnancy through the first year postpartum and birth and developmental outcomes through the infant(s)' first year of life will be described.

There will be a Study Steering Committee and a Publications Steering Committee. The Study Steering Committee should be composed of investigators, external clinical experts not directly involved in the registry and staff from the sponsor with the primary objective of assessing the study quality and conduct, as well as for the scientific quality of the final study report. The Publications Steering Committee should be composed of external experts (clinicians and scientists), patients and representatives of patient associations with the primary objective of driving publications.

### 9.2 Setting

Paediatric and adult participants with FOP who are enrolled in the FOPal registry and have received at least one dose of palovarotene, prescribed as per local label, by their treating physician will be included in the palovarotene-exposed cohort. Paediatric and adult participants with FOP who are enrolled in the FOPal registry and have never received palovarotene, will be included in the palovarotene-unexposed cohort.

Individuals who do not meet the criteria for participation in the FOPal registry study (screen failure) or who withdraw their consent may be rescreened. Rescreened participants should be assigned a new participant number. The informed consent process is described in Section 9.13.

PAGE 37 OF 287

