# 9.2.8 Registry Study Discontinuation/Withdrawal

The participant can withdraw (or be withdrawn if the subject is a child upon legal representative's decision) from the FOPal registry study at any time. The date and primary reason for withdrawal should be recorded in the eCRF as well as whether the participant stopped or not palovarotene for exposed participants.

Should the participant withdraw from the study, no further data will be collected, nevertheless, data collected up to the time of the withdrawal will be kept for analysis, safety and integrity of study results.

The participant will be withdrawn from the FOPal registry study if:

- The participant enrols in any interventional clinical trial for FOP, or,
- For exposed participants: the participant is no longer receiving palovarotene (except if palovarotene is discontinued due to a safety concern or pregnancy, in such cases the participant will be monitored for safety, see Section 11.4 for follow-up of AEs and Section 11.1.3.1 for follow-up of pregnancies).
- For unexposed participants: the participant becomes pregnant or starts a treatment for FOP other than palovarotene. In case the participant starts palovarotene, they should have the option to remain in the registry. Previously unexposed participants starting palovarotene and remaining in the registry will follow the exposed naïve participants schedule (Table 2) from the first marketed palovarotene intake.

Investigators, participants or/and parents may decide to stop the participation in the FOPal registry study at any time without consequences on the normal participant clinical care.

PAGE 50 OF 287

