## 9.6.1 Data Collection

The specific data to be collected at each visit, if available, are summarised in the Schedule of Assessments (Table 2, Table 3 and Table 4).

All relevant data collected as part of routine medical care will be captured using the eCRF by the investigator (patient-reported questionnaires will be completed directly by the participant or proxy on paper and returned to the site for data entry into the eCRF) and transmitted to the sponsor. If some assessments are not routinely performed by the investigator, they will not complete the corresponding sections in the eCRF.

Data will be collected in an eCRF via the internet utilising a secured website. The sponsor and the SP will ensure that the eCRF developed is appropriate to capture the data required by the protocol. The sponsor will ensure that the entrusted SP uses adequate technology to ensure data security transfer and backup.

Each site is required to have a computer and internet connection available for site entry of clinical data. Data entry in the eCRF will be performed by the investigator or by the designated person from their team and to ensure confidentiality and security of the data, all entries into the eCRF will be made under the electronic signature (e-signature) of the person performing the action (username and password). Only sponsor-authorised users will be given access to the eCRF as appropriate for their study responsibilities. All users must have successfully undergone software application training prior to entering data into the eCRF.

Once written informed consent (and assent, if applicable) has been obtained, the eCRF will provide a numeric participant identifier to pseudonymise the data from each participant. Data for each participant must be entered into the eCRF within 5 days of the participant's enrolment, each Follow-Up Visit and the End of Study Visit. Data transmitted will be pseudonymised and will be identified only by the participant number. Only investigating sites will be able to link the numeric identifier to each participant's identity.

In compliance with Good Pharmacoepidemiology Practices (GPP), the participant's medical records should be clearly marked and permit easy identification of their participation in this study.

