# 9.7 Data Analysis

# 9.7.1 Analyses Population Definitions

For the purposes of analyses, the following populations are defined:

- Enrolled Population including all participants who signed the ICF.
- Safety Exposed Population including all enrolled participants who have taken at least one dose of marketed palovarotene at any time before the signed ICF or during the study; A distinction will be made depending on time of start of marketed palovarotene:
  - Palovarotene prevalent users: participants who received palovarotene before or at the time of ICF signed;
  - Palovarotene incident users: participants who started receiving palovarotene after enrolment in the registry. Two time periods will be defined: Period 1 is from enrolment to last day before the first dose of marketed palovarotene; Period 2 is after the first dose of marketed palovarotene.
- Safety Exposed Paediatric Population including all paediatric participants (8 years to less than 18 years of age for girls and 10 years to less than 18 years of age for boys) from the Safety Exposed Population.
- Safety Unexposed Population including all enrolled participants who never received at least one dose of marketed palovarotene before or during their participation in the registry;
- Safety Unexposed Paediatric Population including all paediatric participants (8 years to less than 18 years of age for girls and 10 years to less than 18 years of age for boys) from the Safety Unexposed Population.

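### People who withdraw consent and re-enter get a new participant number while their first record stays in the analysis, and the protocol sets up no link between the two records

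*Protocol*

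**What the plan says.** Section 9.2 (Setting) sets the rescreening rule: "Individuals who do not meet the criteria for participation in the FOPal registry study (screen failure) or who withdraw their consent may be rescreened". The next sentence says: "Rescreened participants should be assigned a new participant number". The rule covers screen failures and consent withdrawals alike.

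Section 9.2.8 says of participants who withdraw that "data collected up to the time of the withdrawal will be kept for analysis, safety and integrity of study results".

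Section 9.7.1 defines the populations by consent and dosing: "Enrolled Population including all participants who signed the ICF", and for the Safety Exposed Population, enrolled "participants who have taken at least one dose of marketed palovarotene at any time before the signed ICF or during the study". The Safety Unexposed Population is those with no marketed dose before or during their participation. None of these definitions says how a person with two numbers is handled.

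Section 9.1 classes anyone dosed before signing consent as non-naïve, for whom "some data will be collected retrospectively from the first dose of marketed palovarotene intake". On identifiers, Section 9.6.1 says: "Only investigating sites will be able to link the numeric identifier to each participant's identity". Section 10.1 speaks of one unique number per participant, assigned at enrolment.

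**The concern.** For a screen failure a new number does little harm beyond the Enrolled Population count. For someone who was enrolled, contributed data and then withdrew, the same rule creates a second participant while the first is still in the analysis set.

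Participant-level incidences, annualised flare-up and fracture frequencies, and the confidence intervals of the weighted exposed-unexposed comparison all treat each participant as a separate person. An unrecognised second record adds to the denominator, can add the same event twice, and removes the independence on which the intervals rest. With minimum cohorts of 67 and 33, one fracture or premature physeal closure counted twice would show in the tables.

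The numbering rule is also an instruction to sites that takes effect when the person returns. An analysis plan written later can define the person as the unit, but it cannot reliably restore a link that was never recorded.

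**Working it through.** The protocol gives no derivation for its minimum of 67 exposed and 33 unexposed, and that figure is not in dispute. The check is mainly a reading of the rules together, for two routes of re-entry.

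**Route 1: exposed person withdraws and re-enters.**
- Status: already dosed before the new consent, so non-naïve under Section 9.1, whatever the status at first entry.
- Collected again from the first marketed dose to the new consent: flare-ups (Section 9.3.2.1), fractures (Section 9.3.2.7), linear height and weight (Table 3 and Section 9.2.7.1) and retrospective important medical events (Table 3, Sections 9.3.2.5 and 11.2.1).
- Index date (Section 9.7.3.4): first marketed dose, hence identical in both records.
- Form: Section 9.3.2.7 puts a fracture after consent on the SAE page, but a non-naïve participant's fracture before consent on a different form. One fracture can therefore sit on the SAE page under the old number and on the retrospective form under the new one.

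Invented timeline to show the mechanism: 2 years on marketed drug before first consent, 1 year followed, 1 year out, then re-entry. The second retrospective period is 2 + 1 + 1 = 4 years, of which 2 + 1 = 3 years are already covered by the first record.

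**Route 2: unexposed person withdraws, starts palovarotene outside the registry and re-enters.**
- Rules for someone who switches without leaving: may stay and follow the naïve schedule (Section 9.2.8); is an incident user with Period 1 before and Period 2 after the first dose (Section 9.7.1); unexposed data are used up to palovarotene intake only if at least 6 months were collected (Section 9.7.3.4).
- Same person under two unlinked numbers: the first record shows no dose during that participation and reads as never exposed. The 6-month minimum is not triggered, so 3 months of unexposed data, say, would enter where a recognised switcher's 3 months would not. The second record has a dose before consent and is classed as a prevalent rather than an incident user. The weighted comparison treats the two as different people.

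**Size.** Inputs: n = 67 or 33 (Section 9.7.2); k re-entries, which is an assumption because the protocol gives no rate. The share of duplicate records is k/n. If k people each supply two identical records among n, the variance of a simple mean is proportional to (n − 2k + 4k)/n² = (n + 2k)/n², against 1/n if all records are taken as independent. The true standard error is then √(1 + 2k/n) times the reported one.
- k = 1: 1/67 = 1.5%, factor √(1 + 2/67) = 1.015; 1/33 = 3.0%, factor √(1 + 2/33) = 1.030.
- k = 3: 3/67 = 4.5%, factor 1.044; 3/33 = 9.1%, factor 1.087.
- k = 5: 5/67 = 7.5%, factor 1.072; 5/33 = 15.2%, factor 1.142.

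Identical records are the extreme case. Records that agree only in part give factors closer to 1.

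**The case against.** The other side has several fair points.

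A reader might infer from Section 9.6.1 that the sponsor cannot link or detect the two records. The text does not say that. It restricts linking a number to an identity, not one record to another. Sites hold the key, monitors verify consent and eligibility against source (Section 9.8.1), and date of birth, gender, diagnosis date and genetic variant are collected where available or permitted (Section 9.3.2.1). In roughly 100 people a match might well be noticed. What stands is that the number alone gives no link and the protocol asks for none.

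A reader might also infer that appearing in both cohorts is an error. It is not, because the protocol plans for unexposed people to become exposed and uses their earlier time. The fault is only that re-entry under a new number avoids the rules governing this.

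Nor is everything recorded again. Table 3 footnote p limits physical examination, growth status, Tanner stage, vital signs, lung function, CAJIS and spinal assessment to the first marketed intake, and footnote n starts ordinary adverse event collection at consent. Most nonserious events would not be repeated. The items listed under Route 1 remain.

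The population definitions speak of participants, and on a person-level reading each individual counts once. That reading is reasonable, but it can be applied only if the two records are known to belong together. Likewise, the phrase "or who withdraw their consent may be rescreened" could be meant for withdrawals before any data exist, but it carries no such limit.

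Finally, an SAP, eCRF guideline or data handling manual that is not shown may deal with duplicates. That would help with the counting, but would not change the site instruction in Section 9.2.

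**Conclusion.** The point holds in a limited form. Followed as written, the numbering rule and the retention rule can put one person into the analysis under two unlinked numbers, with overlapping retrospective time for exposed re-entrants and with the switcher rules bypassed for people who return exposed.

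The size is small per case: 1.5% of the exposed or 3.0% of the unexposed minimum, with a standard error understated by a factor of about 1.02 to 1.03 if the records are identical. It becomes appreciable only if several people re-enter. The protocol gives no re-entry rate. A study of up to 11 years, with about half of each cohort paediatric and fresh consent needed at legal age (Section 9.13), makes some re-entry possible, but any number is an assumption. The analyses are descriptive, so no hypothesis test is at risk; the exposure is to counts, rates and interval widths. It should be corrected because the remedy is nearly free and works only if the link is captured when the person returns.

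**What to change.** - Section 9.2: limit new numbers to screen failures. People who re-enter after withdrawing consent keep their original number or, if the system cannot allow that, the site enters the previous number in a mandatory eCRF field.
- Section 9.7.1: state that the analysis unit is the person, with one index date, no overlapping follow-up and no event counted twice.
- Sections 9.2.8, 9.7.1 and 9.7.3.4: state that someone who moves from unexposed to exposed by re-entry falls under the existing switcher rules, including Periods 1 and 2 and the 6-month minimum.

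The cost is a few sentences and, at most, one eCRF field. No assessment, visit or sample size changes.
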